## 5.2. Rationale

The purpose of this registry-based study is to monitor pregnancies exposed to *Boostrix* with exposure in the recommended window of administration and in line with its indication in the US (i.e., immunization during the third trimester of pregnancy to prevent pertussis in infants younger than 2 months of age). Endpoints were selected based on the current state of knowledge of the safety of *Boostrix* administered to individuals in their third pregnancy trimester and include potentially biologically plausible maternal and neonatal/ early infancy outcomes considering the timing of exposure.

## 6. RESEARCH QUESTION AND OBJECTIVES

The purpose of this study is to examine how selected pregnancy and neonatal/early infant safety outcomes among pregnancies enrolled in the Organization of Teratology Information Specialists (OTIS) / MotherToBaby Pregnancy Registry who were vaccinated with the *Boostrix* Tdap vaccine on or after the 1st day of the 27th week of pregnancy compared to pregnancies unexposed to any Tdap vaccine during the same period, or earlier in pregnancy.

### Study Objectives:

- The **primary objectives** of the study are to evaluate if there is an increased risk for preterm birth, small for gestational age infants, or stillbirth in pregnancies exposed to *Boostrix* vaccination on or after the 1st day of the 27th week of gestation when compared to a cohort of individuals unexposed to any Tdap vaccine during their pregnancy.
- The **secondary objectives** of the study are to evaluate if there is an increased risk of preeclampsia/eclampsia, premature rupture of the membranes, chorioamnionitis, neonatal sepsis, neonatal death, or neonatal intensive care admission for bronchopulmonary dysplasia in pregnancies exposed to *Boostrix* vaccination on or after the 1st day of the 27th week of gestation when compared to a cohort of individuals unexposed to any Tdap vaccine during their pregnancy.

These outcomes were selected based on the current knowledge on the safety of Tdap vaccination during pregnancy, adverse events reported into the Vaccine Adverse Event Reporting System (VAERS) and the biological plausibility for the exposure window of interest.

## 7. RESEARCH METHODS

### 7.1. Study Design

This study is an observational cohort study of pregnancy and neonatal/early infancy safety outcomes in pregnant women in the OTIS/MotherToBaby Pregnancy Registry who received the *Boostrix* vaccine any time on or after the 1st day of the 27th week of pregnancy. The comparator cohort includes pregnant women who received no Tdap vaccine from the first day of LMP to the end of pregnancy. The incidence rates of

maternal and infant outcomes for pregnancies exposed to the *Boostrix* vaccine on or after the 1st day of the 27th week of pregnancy until the end of pregnancy will be compared to those observed in a comparator cohort unexposed to any Tdap vaccine during pregnancy. The target sample size for the study by the end of a four-year recruitment period is 3,000 participants: 1,500 pregnant women in the *Boostrix* vaccine exposure cohort and 1,500 pregnant women in the Tdap vaccine-unexposed comparator cohort.

The study will be conducted by OTIS/MotherToBaby Research Center located at the University of California San Diego. The registry relies on voluntary reporting of pregnancy and exposures by women and health care providers who contact the North American OTIS/MotherToBaby Pregnancy Studies, or the MotherToBaby network.

The study design is appropriate for the study objectives in that mothers are enrolled in the OTIS/MotherToBaby Registry before the outcome of pregnancy is known, direct measures of relative and absolute risk can be computed, and a range of adverse pregnancy outcomes can be evaluated.

The study design includes the identification of women with *Boostrix* vaccine exposure on or after the 1st day of the 27th week of pregnancy, and a comparison group without exposure to a Tdap vaccine from the first day of LMP to the end of pregnancy.

Women who agree to enroll are consented verbally over the telephone and complete the initial telephone interview. Depending on the gestational timing of enrollment, several subsequent telephone interviews are conducted during pregnancy and after birth. Participants are also asked to maintain a pregnancy diary to supplement maternal interview data. Medical records for both the women and infant are obtained and abstracted for information to validate exposures and outcomes. Enrolled women are followed until the completion of pregnancy and follow-up for live born infants in this study will be up to 2 months after birth to determine infant outcomes.

## 7.2. Study Population and Setting

This study will use data that are collected as part of the existing OTIS/MotherToBaby Pregnancy Registry (described further in Section 7.4 Data Source) and housed in a structured database for analysis. The Registry includes pregnant women who reside in the US and allows for direct capture of information from participants through various health interviews as well as complementary information from a pregnancy diary. To obtain information provided by the treating physicians, data are also collected from medical records of pregnant women meeting the inclusion criteria and their infants.

When pregnant women are in contact with the OTIS/MotherToBaby Research Center, enrollment in the OTIS/MotherToBaby Pregnancy Registry is voluntary and requires informed consent of the pregnant woman.

The study population consists of two cohorts of pregnant women:

- **Cohort 1** – *Boostrix* vaccine exposed and

- **Cohort 2** – unexposed (no Tdap vaccine during pregnancy) (See Section 7.5 for sample size).

Participants will be included into the two cohorts based on the following inclusion/exclusion criteria:

### 7.2.1. Inclusion/exclusion criteria

All participants must meet the following criteria to be eligible for inclusion in the study:

- Reside in the US at the time of enrollment
- Enrolled in the OTIS/MotherToBaby Pregnancy Registry and currently pregnant at the time of enrollment on or after 08 March 2004
- Pregnancy ending in either livebirth or stillbirth
- Availability of medical records for that pregnancy including from obstetric provider, hospital of delivery and pediatric provider

The study sample will consist of approximately 600 participants in each cohort that have previously been enrolled in the OTIS/MotherToBaby Pregnancy Registry before the end of pregnancy, have completed their pregnancies with either a livebirth or stillbirth outcome, and have sufficient medical record and exposure data to meet the study objectives. An additional 1,800 participants (900 in each cohort) will be enrolled over four years; these participants will enroll before the end of pregnancy, have completed their pregnancies with either a livebirth or stillbirth outcome, and have sufficient medical record and exposure data to meet the study objectives.

- Selection for consideration for inclusion of the 600 pregnancies in each cohort from those previously enrolled in the OTIS/MotherToBaby Pregnancy Registry will be made solely on the following criteria irrespective of pregnancy outcome
  - Pregnancy continuing as of the 1st day of the 27th week of gestation
  - Availability of data on Tdap vaccination status on or after the 1st day of the 27th week of gestation
  - If vaccinated, data available to document Tdap vaccination brand
  - Availability of the required medical records from obstetric, hospital and pediatric providers
  - Selection starting with most recent year of enrollment until sample size is met

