## Data Analysis

Demographic and other maternal characteristics will be compared between the two cohorts. The outcome analyses include:

1. comparison of proportion of PTBs among those enrolled prior to 37 weeks' gestation and resulting in a live born singleton infant between the *Boostrix*-exposed cohort and the comparison cohort by calculating hazard ratios and associated 95% confidence intervals.
2. comparison of proportion of stillbirths between the *Boostrix*-exposed cohort and the comparison cohort by calculating relative risks and associated 95% confidence intervals.
3. comparison of proportion of SGA infants ( $\leq 10^{\text{th}}$  centile for sex and gestational age) on birth weight, length, and head circumference among live born singletons between the *Boostrix*-exposed cohort and the comparison cohort by calculating relative risks and associated 95% confidence intervals.
4. comparison of proportion of preeclampsia/eclampsia diagnosed after the 1st day of the 27th week of gestation in pregnancies ending in livebirth or stillbirth between the *Boostrix*-exposed cohort and the comparison cohort by calculating relative risks and associated 95% confidence intervals.
5. comparison of proportion of cases of chorioamnionitis in pregnancies ending in livebirth or stillbirth between the *Boostrix*-exposed cohort and the comparison cohort by calculating relative risks and associated 95% confidence intervals.
6. comparison of proportion of PROM occurring after the 1st day of the 27th week of gestation in pregnancies ending in livebirth or stillbirth between the *Boostrix*-exposed cohort and the comparison cohort by calculating relative risks and associated 95% confidence intervals.
7. comparison of proportion of cases of neonatal sepsis occurring in pregnancies ending in live birth including twins or higher order multiples between the *Boostrix*-exposed cohort and the comparison cohort by calculating relative risks and associated 95% confidence intervals.

8. comparison of proportion of neonatal deaths occurring in pregnancies ending in live birth including twins or higher order multiples between the *Boostrix*-exposed cohort and the comparison cohort by calculating relative risks and associated 95% confidence intervals.

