### **Cohort 2: Tdap Vaccine-Unexposed Comparator Group**

#### Inclusion Criteria

- Currently pregnant women at the time of enrollment who were not exposed to any Tdap vaccine from the first day of LMP to the end of pregnancy.
- Currently pregnant women at the time of enrollment who agree to the conditions and requirements of the study including informed consent, the interview schedule and release of medical records.
- Availability of obstetric, delivery and pediatric medical records for the enrollment pregnancy.

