Neonatal death	Secondary Outcome	Maternal report Medical record	Maternal report and medical record documentation of neonatal death. Neonatal death defined as death of a live born infant within 28 days of birth

**Abbreviations:** CDC, Centers for Disease Control and Prevention; LMP, last menstrual period; NCHS, National Center for Health Statistics

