#### **7.5. Study size**

[figure not shown]
The target sample sizes in each of the study cohorts are as follows:

- 1,500 women exposed to *Boostrix* on or after the 1st day of the 27th week of gestation through the end of pregnancy
- 1,500 women unexposed to any Tdap vaccine throughout their pregnancy

Including an estimated 600 eligible participants per cohort already enrolled in the OTIS/MotherToBaby Pregnancy Registry, enrollment of 1,500 participants in each of the cohort groups is planned for completion within 4 years. Participants are eligible to enroll at any time in pregnancy including prior to the gestational timing of the recommended Tdap vaccine. (Examples of gestational timing of enrollment, exposure, and outcome are shown in [Figure 1](#) and [Figure 2](#)). Thus, some initially enrolled pregnancies will no longer be eligible for analysis due to pregnancy losses (spontaneous abortion, elective termination, stillbirth prior to the 27th week of gestation, or lost-to-follow-up). Additionally, some pregnancies will not be eligible for inclusion due to failure to release medical records. The final sample size of 1,500 per cohort will represent all pregnancies that met full inclusion/exclusion criteria. From this sample of livebirths and stillbirths, we conservatively estimate that at least 1,425 in each cohort will represent pregnancies ending in liveborn singleton infants.

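### The condition that pregnancy reach the 27th week is written only for previously enrolled women, so the criteria admit newly enrolled comparators with earlier live births, in conflict with the abstract's follow-up start

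*Protocol*

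**What the plan says.** **Eligibility (section 7.2.1).** The list that all participants must meet sets one condition on how the pregnancy ends: "Pregnancy ending in either livebirth or stillbirth". It gives no minimum gestation. The item beginning "Pregnancy continuing as of the 1" (first day of the 27th week) appears only as a sub-item under "Selection for consideration for inclusion of the 600 pregnancies in each cohort from those previously enrolled". The sentence on new recruits, "An additional 1,800 participants (900 in each cohort) will be enrolled over four years", does not repeat it. Cohort 2 takes women "who were not exposed to any Tdap vaccine from the first day of LMP to the end of pregnancy", and its exclusions add only Tdap receipt and earlier participation. Cohort 1 requires Boostrix on or after the first day of the 27th week. Enrollment may occur at any time in pregnancy (Table 3 footnote 1; section 7.5).

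**Losses (section 7.5).** The text says that "some initially enrolled pregnancies will no longer be eligible for analysis due to pregnancy losses" and lists spontaneous abortion, elective termination, stillbirth before the 27th week and loss to follow-up. Live birth before the 27th week is not listed.

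**Outcomes.** Table 1 limits preterm delivery, stillbirth, small for gestational age (SGA), preeclampsia/eclampsia and premature rupture of membranes (PROM) to the period from the 27th week or vaccination. Section 7.7.1 does so for chorioamnionitis. The Table 1 rows for neonatal sepsis, NICU/BPD and neonatal death have no such limit; the last reads "Neonatal death defined as death of a live born infant within 28 days of birth". Items 7 to 9 of the abstract's data analysis use all pregnancies ending in live birth, for example "comparison of proportion of neonatal deaths occurring in pregnancies ending in live birth including twins or higher order multiples".

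**Follow-up.** The abstract alone starts follow-up for primary and secondary outcomes at vaccination in the exposed and on the first day of the 27th week in comparators.

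**The concern.** The gap is one-sided. Exposed women satisfy the 27th-week condition automatically, because they must be pregnant when vaccinated on or after that day. Previously enrolled comparators satisfy it by rule. Only the 900 newly enrolled comparators (60% of that cohort) can include a live birth before the window. Those are the least mature infants in the study, so any neonatal deaths or BPD admissions among them would fall in the comparator cohort alone.

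The resulting bias is toward apparent protection. In a safety study that direction can mask harm. The outcomes concerned are rare, so a few infants can move the point estimate. The previously enrolled and newly enrolled parts of the same cohort would also follow different entry rules.

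**Working it through.** **1. Is the 27th-week limit stated for newly enrolled comparators?**

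- 7.2.1, all participants: no.
- 7.2.1, sentence on the 900 new participants per cohort: no.
- 7.2.1, Cohort 2 inclusion and exclusion criteria: no.
- 7.5: yes for stillbirth, not for live birth. The final 1,500 are those meeting the full criteria, which leads back to 7.2.1.
- Table 1 and 7.7.1: yes for six outcomes, not for the three neonatal ones.
- Abstract, start of follow-up: implied, but not written as an eligibility rule and not repeated in 7.2.1, Table 1 or 7.7.

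**2. What the follow-up sentence does if it is only a clock.** Let d be the days from birth to the first day of the 27th week.

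- Sepsis must be found within 72 hours of birth, so it counts only if d is at most about 3. Most early-onset sepsis in these births drops out.
- Neonatal death must fall within 28 days of birth, so it can count only if d is below 28 and the infant dies after day d. The earliest deaths drop out; later ones stay.
- The BPD row has no time limit, and infants are followed to 2 months. Admissions after the clock starts can count.

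**3. Possible size for neonatal death.** There is no protocol figure to reproduce. Table 4 does not cover these outcomes, and section 7.5 says only that the other secondary endpoints are expected below 1-2%. Inputs:

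- From the protocol: 900 new comparators, 1,500 per cohort.
- Assumed: share of new comparators delivering live before the window, s = 0.3-0.7%; their neonatal mortality, m = 20-40%; neonatal death risk otherwise, b = 0.1-0.2%.
- Assumed: share f of new comparators enrolled before the window, taken as 1 or 0.5. Later enrollees cannot contribute an early birth.

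Formulas: B = 1,500 × b; E = 900 × f × s × m; relative risk with no vaccine effect = B / (B + E). Removing the early births from the baseline term would change it by at most 6.3 × 0.002 = 0.013 deaths, which is ignored.

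- B = 1,500 × 0.001 = 1.5 to 1,500 × 0.002 = 3.0 deaths.
- f = 1: E = 900 × 0.003 × 0.2 = 0.54 to 900 × 0.007 × 0.4 = 2.52. Relative risk from 1.5/4.02 = 0.37 to 3.0/3.54 = 0.85.
- f = 0.5: E = 0.27 to 1.26. Relative risk from 1.5/2.76 = 0.54 to 3.0/3.27 = 0.92.

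**4. A second set of assumptions**, with f = 1, s = 0.1-0.5%, m = 30-70% and b = 0.1-0.3%: E = 0.27 to 3.15 and B = 1.5 to 4.5. The relative risk runs from 1.5/4.65 = 0.32 to 4.5/4.77 = 0.94. The mid-case (s = 0.3%, m = 50%, b = 0.2%) gives 3.0/4.35 = 0.69.

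Both sets count every death. Under the clock reading, E is smaller and the relative risk closer to 1.

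**The case against.** **The limit may be intended throughout.** A follow-up start that a pregnancy never reaches is naturally read as excluding it. Section 6 describes comparators as unvaccinated in the same period or earlier in pregnancy, which presupposes that they reach the period. Section 7.5 treats stillbirth before the 27th week as ineligible, so leaving out live birth may be incomplete drafting. This stands as evidence of intent. It does not settle the text: the follow-up sentence is in the abstract only, and 7.2.1 states the condition for one group and omits it for the other.

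**Detail may sit elsewhere.** Section 7.3 leaves operational definitions to the SAP, section 7.7.3 allows each outcome its own set of subjects, and Figure 2 is not visible here. Analysis sets may well narrow the denominators. But the protocol itself fixes eligibility, and does so differently for old and new enrollees.

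**The numbers are small and assumed.** This stands. The 0.37 pairs the lowest baseline with the highest extra count. Section 7.5 already concedes limited power: 2 versus 4 deaths in 1,500 each gives a relative risk of 0.5 with a 95% interval of about 0.09 to 2.7. The requirement for pediatric records might also remove some early deaths.

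**Stronger readings.** A reader might infer that early live births certainly enter and count for all three outcomes. The documents do not support that: the abstract can be read as excluding them, and even as a clock it removes most sepsis. Nor do they support a material effect on the other six outcomes, whose events are limited to the window. At the assumed rates, at most 6.3 pregnancies in 1,500 (0.4%) would be added to a denominator.

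**Conclusion.** The point holds as an eligibility gap that conflicts with the abstract's follow-up rule. The written criteria admit newly enrolled comparators with a live birth before the window, and no body section closes this for neonatal death, NICU/BPD or sepsis. For neonatal death and BPD, any bias is toward apparent protection. For sepsis, little remains if the abstract's clock is applied.

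The size cannot be derived from the protocol. The neonatal-death ranges of 0.37-0.85 (all new comparators enrolled before the window) and 0.54-0.92 (half) rest on assumed rates and on every death counting. They show that a few infants can matter and do not predict the result. No figure is offered for BPD or sepsis. The correction is worth making because it is simple and removes a contradiction, but the outcomes affected are secondary and already low in power.

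**What to change.** 1. In section 7.2.1, move the condition that the pregnancy is ongoing on the first day of the 27th week into the list that all participants must meet.
2. In Table 1, limit neonatal sepsis, NICU/BPD and neonatal death to infants born on or after the first day of the 27th week, or the vaccination date if later. State the same limit for their denominators in the analysis text.
3. In section 7.5, add live birth before the 27th week to the pregnancies that become ineligible.

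This extends the protocol's own rule for previously enrolled women to everyone and agrees with the abstract. It deals only with births before the window; comparability within the window is a separate matter. The cost is protocol wording and the loss of a handful of newly enrolled pregnancies (900 × 0.3-0.7% = 2.7 to 6.3 under the assumptions above, fewer if many enroll later).

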## 4. MILESTONES

Milestone	Planned date
Start of data collection	01 March 2023 
End of data collection	31 December 2027 
Study enrollment report	Monthly until end of recruitment
Annual status report of Postmarketing Requirements/Commitments due By:	06 December 2023 06 December 2024 06 December 2025 06 December 2026 06 December 2027
Registration in the European Union post-authorization studies (EU PAS) register	To be confirmed
Final study report submission	31 August 2028

 Pregnant women participating in the OTIS/MotherToBaby Pregnancy Registry on or after 08 March 2004 are eligible for study inclusion; however, selection of the 600 eligible pregnancies in each cohort from those enrolled prior to 01 March 2023 will be prioritized to include most recent years of enrollment. The start of data collection is defined as the planned date for starting data review for the first annual progress report.

 The end of data collection is defined as the planned date on which the analytic dataset will be first completely available; the analytic dataset is the minimum set of data required to perform the statistical analysis for the study objectives.

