To date, no specific safety concerns have been identified for Tdap maternal immunization (Vygen-Bonnet, 2020; Hall, 2020; Mohammed, 2021; Fakhraei, 2021), including *Boostrix*-specific studies (Perrett, 2020a; Perrett, 2020b; Petousis-Harris, 2019; Sancovski, 2019; Tseng, 2022).

The *Boostrix*-specific studies also include a large observational study (NCT03463577) conducted in the US by Kaiser Permanente Southern California (KPSC) in which the safety of *Boostrix* was assessed in 16,606 pregnant individuals who received *Boostrix* on or after the 27th week of pregnancy in 2018–19 compared with a historical cohort of individuals who were pregnant in 2012–14 and did not receive any Tdap vaccine during their pregnancy (Tseng, 2022). The study assessed a wide range of fetomaternal and neonatal outcomes. Overall, the study results support the safety of *Boostrix*.

For *Boostrix* specifically, the study conducted at KPSC found an elevated adjusted relative risk (aRR) for intra-uterine infection (aRR = 1.28, 98.75% confidence interval [CI]: 1.12–1.47) within the pre-determined significance levels (the upper limit of the 98.75% CI for the aRR was below 2) and this increase was consistent with the background increasing trend of this diagnosis among all pregnant individuals at KPSC since 2011 (before the study vaccination period). This may reflect improved obstetric care. The other *Boostrix*-specific studies, including a clinical trial in pregnant subjects (Perrett, 2020a) and a population-based observational study in New Zealand (Griffin, 2018), did not find evidence of an increased risk.

The new registry study is intended to add to the existing safety data for *Boostrix* as compared to the US pregnancy registry EPI-PERTUSSIS-028 VS US PR (201327) and will be established in collaboration with the OTIS/MotherToBaby Research Center, an organization with well-established measures proven to efficiently retain participants and provide more complete and meaningful data.

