Upon study initiation, eligible participants from existing OTIS/MotherToBaby Registry data will be identified, and recruitment of newly enrolled participants is expected to continue for 4 years, or until the target of 1,500 women exposed to *Boostrix* is reached, whichever comes first. After recruitment of the last participant, infant follow-up will continue for 2 months after the last live birth. Given the prevalence of *Boostrix* vaccination in pregnancy, and annual rates of enrollment of between 1,500 and 2,000 pregnant women overall in all MotherToBaby Pregnancy Studies, the planned four-year

recruitment period for this study is reasonable. However, should recruitment numbers fail to meet targets, specific additional awareness and marketing efforts will be initiated by the MotherToBaby research team.

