### 7.7.2. Sensitivity analyses

To address changes over time in diagnostic criteria for preeclampsia/eclampsia, year of enrollment will be considered as a potential confounder in analyses. However, an additional sensitivity analysis will be conducted by stratifying the analysis on data collection prior to and after the year the diagnostic criteria modifications were implemented.

In addition, if major discrepancies are identified by descriptive analysis of baseline characteristics and outcomes for the participants previously enrolled in the OTIS/MotherToBaby Pregnancy Registry and the participants newly enrolled over 4

years, further exploratory stratified analyses could be conducted, provided the sample size allows for it.

To address potential unmeasured confounding associated with being a “healthy vaccinator”, a second sensitivity analysis will be conducted restricting the sample in each cohort to those who received the recommended influenza vaccination in pregnancy. This ensures that both the exposed and comparator groups were at least compliant with one vaccine recommendation in pregnancy.

Although major birth defects are not expected to be causally related to Tdap vaccination exposure that takes place long after completion of embryogenesis when most major birth defects occur, major birth defects will be considered as a potential confounder in analyses. For example, prenatal diagnosis of a major birth defect could influence willingness to receive a Tdap vaccination later in pregnancy. In turn the major birth defect could independently influence risk of stillbirth, PTB or SGA. To further address this issues, a third sensitivity analysis will be conducted excluding infants in both cohorts with documented major birth defects.

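### The historical part of each cohort is filled separately from the latest year backwards, so enrollment years may differ between cohorts, and adjustment for year is not assured

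*Protocol*

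**What the plan says.** **Selection.** Protocol Section 7.2.1: "The study sample will consist of approximately 600 participants in each cohort that have previously been enrolled". These women are chosen only on the listed criteria, irrespective of pregnancy outcome, and the last criterion is "Selection starting with most recent year of enrollment until sample size is met". The first footnote in Section 4 repeats that selection of the 600 per cohort "will be prioritized to include most recent years of enrollment". Neither place asks for the two cohorts to have the same spread of years. Vaccinated women must also have a documented brand, and only *Boostrix* given on or after the first day of week 27 counts as exposure.

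**New recruitment.** Section 7.2.1: "An additional 1,800 participants (900 in each cohort) will be enrolled over four years".

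**Calendar time in the analysis.** Section 7.7.2 says that "year of enrollment will be considered as a potential confounder in analyses". The sentence is introduced by the change in preeclampsia/eclampsia criteria, and the planned stratification by period concerns that outcome. A stratified analysis of earlier against new enrollees is optional, exploratory and conditional on sample size. Year of enrollment is not in Table 2. Section 7.7.1 admits a variable to the propensity score only if it meets all three of these criteria: a change of 10% or more in the exposure odds ratio, a standardized mean difference above 0.1, and p<0.2 for association with the outcome in the unexposed.

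**A trend already met.** Section 5.1 reports a raised estimate for intra-uterine infection in an earlier *Boostrix* study and says "this increase was consistent with the background increasing trend of this diagnosis among all pregnant individuals at KPSC since 2011".

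**The concern.** Two pools filled separately to the same count from the same starting year reach equally far back only if eligible women accrue at the same rate in both. The eligibility filters differ, so there is no reason to expect that. Anything that changes with calendar time (diagnostic practice, coding, obstetric care) then becomes partly confounded with vaccination in 40% of the sample.

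The natural protection is adjustment for year, but the screen works against it. A calendar-time bias of a few percent cannot move the odds ratio by 10%, so the rule removes year in just the cases where the bias is modest. Scores are built separately for each endpoint, so year may be adjusted for in one outcome and not in another. Chorioamnionitis is the most exposed: it is closely related to the diagnosis for which the protocol cites a background trend, and it is one of the three endpoints for which Table 4 gives power.

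**Working it through.** **1. The plan's own figure.** Table 4, chorioamnionitis: 1,469 per group, 3% against 5.1% (RR 1.7), two-sided alpha 0.05, Fisher's exact test, 80% power. Simulated Fisher power (20,000 runs) is 80.5%; the normal approximation gives 82.3%. The row reproduces and serves as the base case.

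**2. Historical share.** 600 / 1,500 = 0.40. The other 900 / 1,500 = 0.60 is recruited over the same four years.

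**3. How far back each cohort reaches.** Years needed = 600 / (annual enrollment × share of enrollees in that cohort × usable fraction).

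- From the protocol: 1,500 to 2,000 enrollees a year (Section 7.2.2); 55% Tdap uptake, both brands together (Section 5.1).
- Assumed, because the protocol does not give them: *Boostrix* brand share 30–70%; fraction with usable records 10–100%; an alternative registry uptake of 80%; constant yearly rates.

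Example with 1,500 a year, 55% uptake, 30% brand share and all records usable:

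- exposed: 600 / (1,500 × 0.55 × 0.30) = 600 / 247.5 = 2.4 years
- unexposed: 600 / (1,500 × 0.45) = 600 / 675 = 0.9 years
- gap in mean enrollment year: (2.42 − 0.89) / 2 = 0.77 years, exposed older

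| Usable fraction | Gap at 55% uptake (exposed older), years | Gap at 80% uptake (unexposed older), years |
|---|---|---|
| 100% | 0.06–0.77 | 0.13–0.64 |
| 30% | 0.19–2.56 | 0.42–2.14 |
| 10% | 0.56–7.68 | 1.25–6.43 |

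The extremes of the last row need 20 to 24 years of enrollment, which runs past the March 2004 limit, so 600 could not be reached there. Constant rates are also doubtful before the 2012 recommendation. The first two rows are the more useful guide.

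**4. What a gap does to chorioamnionitis.** Take the whole earlier estimate of 1.28 as trend over an assumed 5.5 years (mid-2013 to late 2018): 1.28^(1/5.5) − 1 = 4.6% a year. With no true effect, the whole-cohort RR is 0.6 + 0.4 × 1.28^(gap/5.5). A positive gap means that the unexposed are older.

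| Gap, years | Spurious RR | OR at 3% base rate | Chance of a false upward signal |
|---|---|---|---|
| 0 | 1.00 | 1.00 | 2.5% |
| 1 | 1.02 | 1.02 | 3.1% |
| 3 | 1.06 | 1.06 | 4.6% |
| 5 | 1.10 | 1.10 | 6.8% |
| 8 | 1.17 | 1.18 | 12.1% |

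If the exposed are older, a rising trend lowers the RR instead. At 3 years: 0.6 + 0.4 / 1.144 = 0.95. At 5 years: 0.6 + 0.4 / 1.252 = 0.92.

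**5. Would the screen keep year?** The 10% rule is missed at 1 and 3 years in either direction and is borderline at 5 years upward. The third criterion adds a hurdle: 3% of 1,469 is about 44 comparator events on which to reach p<0.2.

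**The case against.** The strongest reply is that the effect is probably small and partly handled. Both selections start in the same latest year, so the windows always overlap. Taking recent women first is itself a guard against old comparators. With all records usable, the gap stays below 0.8 years and the bias below about 2%, against a design built to detect relative risks of 1.4 to 1.7. Section 7.7.2 does name year as a potential confounder. Section 7.7.1 promises a confounder list for each outcome, and the SAP may add detail.

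Most of this stands, and it limits the point. It does not remove it, because the screen is stated in the protocol and applies in addition to the list, and because the selection rule is a protocol rule.

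A reader might infer more than the documents support:

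- **That the two cohorts come from different calendar years.** They overlap by construction.
- **That the design repeats the bias of the earlier study.** That study compared 2018–19 with 2012–14, with no overlap. Here 60% of each cohort is recruited over the same four years.
- **That the relative risk of 1.28 measures the problem.** The protocol says only that the increase was consistent with a trend. At 55% uptake the exposed would be the older group, so a rising trend would push the estimate down.
- **That comparators will predate vaccination in pregnancy**, because women are eligible if "currently pregnant at the time of enrollment on or after 08 March 2004". That date is a floor, and selection runs backwards from the latest year.
- **That new recruitment is not concurrent**, because "recruitment of newly enrolled participants is expected to continue for 4 years, or until the target of 1,500 women exposed to" *Boostrix* is reached. This ends new recruitment as a whole; nothing says that one cohort closes before the other.

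**Conclusion.** The point holds in a limited form. The selection rule does not ensure similar enrollment-year distributions in the historical 40% of the two cohorts, and adjustment for year is not assured. Neither the size nor the sign of the gap is fixed by the protocol: under the assumed ranges it runs from under 0.1 year to several years, in either direction. On the trend illustration, gaps of 1 to 3 years leave a bias of about 2% to 6% that the 10% rule would not catch. A false upward signal then has a probability of 3.1% to 4.6% instead of 2.5% if the comparators are older; a real increase would be partly masked if the exposed are older.

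These sizes rest on the assumed brand share, usable fraction and registry uptake, on constant yearly rates, and on reading all of 1.28 as trend over 5.5 years. They show scale and do not predict a result. This is a cheap improvement, not a flaw that invalidates the comparison.

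**What to change.** 1. In Section 7.2.1 and the Section 4 footnote, select the historical women so that both cohorts have similar enrollment-year distributions. Frequency-match in bands of 1 to 2 years, anchored on whichever cohort is scarcer, still starting from the most recent years.
2. In Sections 7.7.1 and 7.7.2, keep year of enrollment in every propensity score and in the marginal structural model for preterm birth, regardless of the three-part screen, and add it to Table 2.
3. Report the enrollment-year distribution by cohort, separately for historical and new enrollees, in the annual and final reports.

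The cost is a changed query on an existing database, one more covariate in each model and one descriptive table. The small downside is that some recent women from the larger pool are replaced by slightly older ones.
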